5.3 Lifestyle Considerations

5.3.1 Contraception

Pembrolizumab may have adverse effects on a fetus in utero. Refer to Appendix 5 for approved methods of contraception.

Participants should be informed that taking the study medication may involve unknown risks to the fetus (unborn baby) if pregnancy were to occur during the study. In order to participate in the study, participants of childbearing potential must adhere to the contraception requirement (Appendix 5) from the day of study medication initiation (or 14 days prior to the initiation of study medication for oral contraception) throughout the study period up to 120 days after the last dose of study medication. If there is any question that a participant of childbearing potential will not reliably comply with the requirements for contraception, that participant should not be entered into the study.

5.3.2 Pregnancy

If a participant inadvertently becomes pregnant while on treatment with pembrolizumab, the participant will be immediately discontinued from study intervention. The site will contact the participant at least monthly and document the participant's status until the pregnancy has been completed or terminated. The outcome of the pregnancy will be reported to the Sponsor without delay and within 24 hours if the outcome is a serious adverse experience (eg, death, abortion, congenital anomaly, or other disabling or life-threatening complication to the mother or newborn). The study Investigator will make every effort to obtain permission to follow the outcome of the pregnancy and report the condition of the fetus or newborn to the Sponsor. If a male participant impregnates his female partner, the study personnel at the site must be informed immediately and the pregnancy must be reported to the Sponsor and followed as described in Section 8.4.5.

5.3.3 Use in Nursing Women

It is unknown whether pembrolizumab is excreted in human milk. Since many drugs are excreted in human milk, and because of the potential for serious adverse reactions in the nursing infant, participants who are breastfeeding are not eligible for enrollment.

5.4 Screen Failures

Screen failures are defined as participants who consent to participate in the clinical study, but are not subsequently randomized in the study. A minimal set of screen failure information is required to ensure transparent reporting of screen failure participants to meet the Consolidated Standards of Reporting Trials (CONSORT) publishing requirements and to respond to queries from regulatory authorities. Minimal information includes demography, screen failure details, eligibility criteria, and any AEs or SAEs meeting reporting requirements as outlined in the data entry guidelines.

5.5 Participant Replacement Strategy

A participant who discontinues from study intervention or withdraws consent will not be replaced.

6 STUDY INTERVENTION

Study intervention is defined as any investigational intervention(s), marketed product(s), placebo, or medical device(s) intended to be administered to a study participant according to the study protocol.

Clinical supplies of pembrolizumab will be packaged to support enrollment. Clinical supplies will be affixed with a clinical label in accordance with regulatory requirements.

6.1 Study Intervention(s) Administered

The study interventions to be used in this study are outlined in [Table 3](#).

Table 3 Study Interventions

Arm Name	Arm Type	Intervention Name	Type	Dose Formulation	Unit Dose Strength(s)	Dosage Level(s)	Route of Administration	Regimen/ Treatment Period/ Vaccination Regimen	Use	IMP or NIMP/ AxMP	Sourcing
Arm 1	Experimental	Pembrolizumab	Drug	Vial	25 mg/mL	200 mg	IV Infusion	Day 1 of each cycle	Test Product	IMP	Centrally by Sponsor
Arm 2	Placebo Comparator	Placebo	Drug	Vial	Normal Saline, 0.90% w/v	0 mg	IV Infusion	Day 1 of each cycle	Placebo	IMP	Provided locally by the study site, subsidiary, or designee

EEA=European Economic Area; IMP = investigational medicinal product; IV = intravenous; NIMP/AxMP=noninvestigational/auxiliary medicinal product; w/v = weight/volume.
 
The classification of IMP and NIMP/AxMP in this table is based on guidance issued by the European Commission and applies to countries in the EEA. Country differences with respect to the definition/classification of IMP and NIMP/AxMP may exist. In these circumstances, local legislation is followed.
											

All study interventions will be administered on an outpatient basis.

All products indicated in [Table 3](#) will be provided centrally by the Sponsor or locally by the study site, subsidiary or designee, depending on local country operational or regulatory requirements with the exception of placebo (normal saline), which will be provided locally.

For any commercially available product that is provided by the study site, subsidiary, or designee, every attempt will be made to source these supplies from a single lot/batch number. The study site is responsible for recording the lot number, manufacturer, and expiry date for any locally purchased product as per local guidelines unless otherwise instructed by the Sponsor.

Refer to Section 8.1.8 for details regarding administration of the study intervention.

6.2 Preparation/Handling/Storage/Accountability

6.2.1 Dose Preparation

Details on preparation and administration of pembrolizumab are provided in the Pharmacy Manual.

6.2.2 Handling, Storage, and Accountability

The investigator or designee must confirm appropriate temperature conditions have been maintained during transit for all study intervention received, and any discrepancies are reported and resolved before use of the study intervention.

Only participants enrolled in the study may receive study intervention, and only authorized site staff may supply or administer study intervention. All study interventions must be stored in a secure, environmentally controlled, and monitored (manual or automated) area in accordance with the labeled storage conditions with access limited to the investigator and authorized site staff.

The investigator, institution, or the head of the medical institution (where applicable) is responsible for study intervention accountability, reconciliation, and record maintenance (ie, receipt, reconciliation, and final disposition records).

For all study sites, the local country Sponsor personnel or designee will provide appropriate documentation that must be completed for drug accountability and return, or local discard and destruction if appropriate. Where local discard and destruction is appropriate, the investigator is responsible for ensuring that a local discard/destruction procedure is documented.

The study site is responsible for recording the lot number, manufacturer, and expiry date for any locally purchased product (if applicable) as per local guidelines unless otherwise instructed by the Sponsor.

The investigator shall take responsibility for and shall take all steps to maintain appropriate records and ensure appropriate supply, storage, handling, distribution, and usage of study interventions in accordance with the protocol and any applicable laws and regulations.

6.3 Measures to Minimize Bias: Randomization and Blinding

6.3.1 Intervention Assignment

Intervention allocation/randomization will occur centrally using an interactive response technology (IRT) system. There are 2 study intervention arms. Participants will be assigned randomly in a 1:1 ratio to pembrolizumab or placebo.

CCI

6.3.3 Blinding

A double-blinding technique will be used. Pembrolizumab and placebo will be prepared and/or dispensed in a blinded fashion by an unblinded pharmacist or qualified study site personnel. The participant, the investigator, and Sponsor personnel or delegate(s) who are involved in the study intervention administration or clinical evaluation of the participants are unaware of the intervention assignments.

6.4 Study Intervention Compliance

Administration of study medication(s) will be monitored by the investigator and/or study staff. The total volume of study medication infused will be compared with the total volume prepared to determine compliance with each dose administered.

Interruptions from the protocol-specified treatment plan for more than 12 weeks between pembrolizumab doses for nondrug-related or administrative reasons require consultation

between the investigator and the Sponsor and written documentation of the collaborative decision on participant management.

If there are interruptions in the study intervention schedule or infusion was stopped, the details of and reason for any interruption or cessation of study intervention infusion will be documented in the participant's medical record.

Refer to Section 6.6.1 for Dose Modification and Toxicity Management Guidelines for irAEs associated with pembrolizumab monotherapy, coformulations, or IO combinations and for other allowed dose interruptions.

6.5 Concomitant Therapy

Medications or vaccinations specifically prohibited in the exclusion criteria are not allowed during the ongoing study. If there is a clinical indication for any medication or vaccination specifically prohibited, discontinuation from study therapy or vaccination may be required. The investigator should discuss any questions regarding this with the Sponsor's Clinical Director. The final decision on any supportive therapy or vaccination rests with the investigator and/or the participant's primary physician. However, the decision to continue the participant on study intervention requires the mutual agreement of the investigator, the Sponsor, and the participant.

The following medications and vaccinations are prohibited during the study:

- Antineoplastic systemic chemotherapy or biological therapy.
- Immunotherapy not specified in this protocol.
- Chemotherapy not specified in this protocol.
- Investigational agents other than pembrolizumab.
- Radiation therapy.
- Oncologic surgical therapy.
- Live vaccines within 30 days prior to the first dose of study intervention and while participating in the study. Examples of live vaccines include, but are not limited to, the following: measles, mumps, rubella, varicella/zoster, yellow fever, rabies, BCG, and typhoid vaccine. Seasonal influenza vaccines for injection are generally killed virus vaccines and are allowed; however, intranasal influenza vaccines (eg, FluMist®) are live attenuated vaccines and are not allowed. Refer to Appendix 7 for country-specific requirements.

Note: Any licensed COVID-19 vaccine (including for Emergency Use) in a particular country is allowed in the study as long as they are mRNA vaccines, adenoviral vaccines, or inactivated vaccines. These vaccines will be treated just as any other concomitant therapy.

Investigational vaccines (ie, those not licensed or approved for Emergency Use) are not allowed.

- Systemic glucocorticoids except when used for the following purposes.
 - To modulate symptoms of an AE that is suspected to have an immunologic etiology
 - To premedicate for IV contrast allergies
 - To treat COPD exacerbations (only short-term oral or IV use in doses >10 mg/day prednisone equivalent)
 - For chronic systemic replacement not to exceed 10 mg/day prednisone equivalent
- Other glucocorticoid use except when used for the following purposes:
 - For topical use or ocular use
 - Intraarticular joint use
 - For inhalation in the management of asthma or chronic obstructive pulmonary disease
- DAA HCV therapy with potential drug interactions with study intervention that need to be continued post-randomization.

At each visit, participants should be questioned about any new drug they are taking.

To minimize the risk of adverse drug interactions, every effort should be made to limit the number of concomitant drugs to those that are truly essential.

Drugs known to be hepatotoxic (ie, drugs with a warning of hepatotoxicity in the package insert) should be avoided during the Screening and Treatment Phase of this study. Investigators are encouraged to review each medication for potential hepatotoxicity by searching the www.livertox.nih.gov website.

Listed below are examples known hepatotoxic drugs that should be avoided:

Etifoxine

Isoniazid

Nitrofurantoin

Ketoconazole

Amiodarone

Phenytoin

Herbal supplements or alternative medicines should also be avoided during the Screening and Treatment Phase of this study.

Participants who, in the assessment of the Investigator, require the use of any of the aforementioned treatments for clinical management should be removed from the study.

All treatments that the investigator considers necessary for a participant's welfare may be administered at the discretion of the investigator in keeping with the community standards of medical care. All concomitant medication will be recorded on the eCRF including all prescription, over-the-counter (OTC) products, and IV medications and fluids. If changes occur during the study period, documentation of drug dosage, frequency, route, and date should also be included on the eCRF.

All concomitant medications received within 28 days prior to the first dose of study intervention and up to 30 days after the last dose of study intervention should be recorded. Concomitant medications administered 30 days after the last dose of study intervention should be recorded for SAEs and events of clinical interest (ECIs) as defined in Section 8.4.7.

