Duration of Participation	
Each participant will participate in the study for approximately 6 years from the time the participant provides documented informed consent through the final contact. After a screening phase of 28 days, each participant will be receiving assigned intervention to 17 administrations (approximately 1 year). After the end of treatment, each participant will be followed for 30 days for AEs. Serious adverse events will be collected for 90 days after the end of treatment or for 30 days after the end of treatment if the participant initiates new anticancer therapy, whichever is earlier.
 
Each participant will participate in the study from the time that the participant provides documented informed consent through the final protocol-specified contact.
 
After a screening phase, each participant will be assigned to receive study intervention (pembrolizumab or placebo) until disease recurrence is documented by investigator and verified by BICR, unacceptable adverse event(s) (AEs), intercurrent illness that prevents further administration of treatment, investigator's decision to discontinue the participant, administrative reasons requiring cessation of treatment, or until the participant has received 17 administrations of pembrolizumab or placebo (approximately 1 year).
 
Disease recurrence will be documented by investigator radiographically (with site radiologist) and will be verified by BICR. Disease recurrence will be verified by BICR prior to DC of study intervention. No cross-over is allowed in this study. For participants who DC for reasons other than BICR-verified disease recurrence or BICR-verified intra-hepatic recurrence, imaging should continue to be performed as if on study until extra-hepatic disease recurrence has been verified by BICR. Disease recurrence can also be confirmed with pathology if required per the site's standard of care.
 
After the end of study treatment, each participant will be followed for the occurrence of AEs and spontaneously reported pregnancy as described under Section 8.4.4.
 
Participants who initiate a new non-study cancer treatment should continue to have post-treatment distant metastases-free survival (DMFS) follow-up until extra-hepatic disease recurrence is documented by investigator (radiographically and/or with subsequent pathology) and verified by BICR.
 
All participants will be followed for overall survival until death, withdrawal of consent, or the end of the study.

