7 DISCONTINUATION OF STUDY INTERVENTION AND PARTICIPANT WITHDRAWAL

7.1 Discontinuation of Study Intervention

Discontinuation of study intervention does not represent withdrawal from the study.

As certain data on clinical events beyond study intervention discontinuation may be important to the study, they must be collected through the participant's last scheduled follow-up, even if the participant has discontinued study intervention. Therefore, all participants who discontinue study intervention prior to completion of the protocol-specified treatment period/vaccination will still continue to be monitored in the study and participate in the study visits and procedures as specified in Section 1.3 (SoA) and Section 8.11.3 (Participants Discontinued from Study Intervention but Continuing to be Monitored in the Study) unless the participant has withdrawn from the study (Section 7.2).

Participants may discontinue study intervention at any time for any reason or be discontinued from the study intervention at the discretion of the investigator should any untoward effect occur. In addition, a participant may be discontinued from study intervention by the investigator or the Sponsor if study intervention is inappropriate, the study plan is violated, or for administrative and/or other safety reasons. Specific details regarding procedures to be performed at study intervention discontinuation are provided in Section 8.1.9.

A participant must be discontinued from study intervention but continue to be monitored in the study for any of the following reasons:

The participant or participant's legally acceptable representative requests to discontinue study intervention

AEs described in the dose modification table that require discontinuation of study intervention (refer to Section 6.6.1).

After prolonged study intervention interruption that prohibits restarting study intervention if agreed upon with the Sponsor.

The participant has a medical condition or personal circumstance which, in the opinion of the investigator and/or Sponsor, placed the participant at unnecessary risk from continued administration of study intervention.

The participant has a confirmed positive serum pregnancy test.

The participant is receiving any prohibited concomitant medication requiring withdrawal (refer to Section 6.5).

Participant has any of the following non-overdose hepatic ECIs:

- ALT $>20 \times \text{ULN}$ (confirmed within 1 week)

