7.2 Participant Withdrawal From the Study

A participant must be withdrawn from the study if the participant or participant’s legally acceptable representative withdraws consent from the study.

If a participant withdraws from the study, they will no longer receive study intervention or be followed at scheduled protocol visits.

Specific details regarding procedures to be performed at the time of withdrawal from the study, as well as specific details regarding withdrawal from future biomedical research, are outlined in Section 8.1.9. The procedures to be performed should a participant repeatedly fail to return for scheduled visits and/or if the study site is unable to contact the participant are outlined in Section 7.3.

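### Section 6.5 tells sites to remove from the study anyone who needs a listed treatment, which contradicts Sections 7.1 and 7.2 and can end RFS and OS follow-up early

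*Combined protocol and SAP*

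**What the plan says.** Section 6.5 contains two lists. The first opens with "The following medications and vaccinations are prohibited during the study" and covers anticancer drugs, immunotherapy, radiation, oncologic surgery, live vaccines, systemic glucocorticoids outside named exceptions, and certain HCV antivirals. The second covers drugs with a hepatotoxicity warning, and then adds: "Herbal supplements or alternative medicines should also be avoided during the Screening and Treatment Phase of this study". The sentence at issue comes straight after the second list: participants who, in the investigator's assessment, "require the use of any of the aforementioned treatments for clinical management should be removed from the study". The opening of the same section is milder. Where a prohibited product is clinically indicated, it says only that "discontinuation from study therapy or vaccination may be required".

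Section 7.1 states: "A participant must be discontinued from study intervention but continue to be monitored in the study for any of the following reasons". One of the reasons it lists is "The participant is receiving any prohibited concomitant medication requiring withdrawal (refer to Section 6.5"). It also says that stopping study intervention is not the same as leaving the study.

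Section 7.2 names one mandatory ground for leaving, which is withdrawal of consent, and gives the consequence: "If a participant withdraws from the study, they will no longer receive study intervention or be followed at scheduled protocol visits".

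The synopsis follows every participant for OS until death, consent withdrawal or study end. It also says: "Participants who initiate a new non-study cancer treatment should continue to have post-treatment distant metastases-free survival (DMFS) follow-up".

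On analysis, Section 9.5.1 defines ITT as all randomized participants, and Table 8 censors OS at the date last known alive. The RFS censoring rules (Table 7) are redacted.

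**The concern.** Sections 6.5 and 7.1 cover the same trigger, and 7.1 points to 6.5 by number, yet they give opposite instructions about staying in the study. A site cannot follow both literally.

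The difference matters because an ITT analysis needs outcomes from everyone randomized, including those who stop study intervention. A participant removed under 6.5 would be censored at the last contact for OS. If removal came before a recurrence was documented, the RFS event would be lost as well. The need for a listed treatment may mark recurrence, infection or worsening liver disease. Censoring at that moment need not be independent of the outcome, and it could differ between arms.

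**Working it through.** The plan states no figure on this point, so there is none to reproduce. The check is a comparison of the text, followed by an illustration of size.

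**1. Text side by side.**

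| Place | What happens to the participant |
|---|---|
| 6.5, opening | Study therapy may have to stop; leaving the study is not mentioned |
| 6.5, sentence after the lists | Removed from the study |
| 7.1 | Study intervention stops; monitoring continues |
| 7.2 | Mandatory withdrawal only if consent is withdrawn |
| Synopsis | OS follow-up for all; follow-up continues after new cancer treatment |
| 8.11.3 | Encouraged to attend all remaining visits |

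The one sentence in 6.5 is the outlier.

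**2. Scope.** The sentence may refer to both lists or only to the second. The second list applies to the Screening and Treatment Phase, which includes about one year of treatment. Section 7.1 names only prohibited medication. For the second list, the conflict therefore runs through the general rules in 7.1 and 7.2.

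**3. RFS illustration, removals in year 1.** Inputs from Section 9.9.1: control median 33.8 months, so λ = ln 2 / 33.8 = 0.0205 per month; 36-month enrollment; 950 participants, 1:1. Assumptions: exponential times; cut at 72 months from first entry; 20% of each arm have hazard k × λ with k = 1.5 or 2; only they are removed, each with probability q / 0.20, at a uniform time in months 0 to 12. Hazard ratios come from a one-covariate Cox model on 400,000 simulated participants, with events scaled to 950. Each pair below uses the same simulated people, with full follow-up and then with removals.

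| Removed, placebo / pembrolizumab | Assumed HR | HR full → removed (k = 1.5; k = 2) | Events lost (k = 1.5; k = 2) |
|---|---|---|---|
| 2% / 2% | 1.0 | 1.001 → 1.001; 1.000 → 1.000 | 655 − 643 = 12; 670 − 657 = 13 |
| 2% / 2% | 0.75 | 0.750 → 0.750; 0.760 → 0.759 | 607 − 595 = 12; 623 − 610 = 13 |
| 2% / 10% | 1.0 | 1.002 → 0.979; 0.993 → 0.958 | 656 − 619 = 37; 672 − 633 = 39 |
| 2% / 10% | 0.75 | 0.755 → 0.736; 0.755 → 0.725 | 609 − 575 = 34; 625 − 588 = 37 |
| 5% / 15% | 1.0 | 1.002 → 0.974; 1.002 → 0.953 | 655 − 594 = 61; 671 − 607 = 64 |

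In the table, equal removal loses about 2% of events (12/655) with no bias. The largest shift is 1.002 − 0.953 = 0.049, with 64/671 = 9.5% of events lost, and it requires unequal removal.

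**4. OS illustration, removal at recurrence (broad reading).** Assumptions: control recurrence hazard 0.9λ, multiplied by 0.75 on pembrolizumab; death without recurrence 0.1λ in both arms; median survival after recurrence 24 or 36 months; cut at month 84; a share s of recurring participants removed at recurrence, equal by arm.

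| s | Deaths, HR (24 months) | Deaths, HR (36 months) |
|---|---|---|
| 0 | 440, 0.826 | 367, 0.843 |
| 5% | 422, 0.825 | 353, 0.843 |
| 25% | 349, 0.821 | 294, 0.840 |
| 50% | 258, 0.821 | 221, 0.837 |
| 100% | 74, 0.999 | 75, 0.999 |

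At s = 25%, 91/440 = 21% (24 months) or 73/367 = 20% (36 months) of deaths go uncounted, while the hazard ratio moves by at most 0.005. The survival curves are affected more. In a similar run (recurrence HR 0.70, 8% of control first events being deaths, 24 months after recurrence), control 4-year OS rose from 0.653 to 0.669 with 10% removed and from 0.652 to 0.706 with 30% removed.

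**The case against.** The best reply is that the rest of the protocol keeps these people in. Section 7.1 lists recurrence as a reason to stop intervention while monitoring continues. The schedule of activities collects anticancer therapy status throughout follow-up. Section 8.2.1.2 continues imaging after intrahepatic recurrence. Section 8.11.2.2 records later anticancer treatment, and 8.11.2.3 continues survival contacts. Section 8.11.4 allows vital-status checks before analyses. The disputed sentence may cover only hepatotoxic and herbal products. Steroids for suspected immune-related events are exempt, which closes the most obvious route to imbalance between arms.

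Most of this stands, and it limits what can be claimed. A reader might infer that everyone who recurs and starts anticancer therapy leaves the study, so that the OS comparison collapses (the 100% row). The documents do not support that: a site acting this way would breach several other sections, so the row is only an extreme bound. A reader might also infer that the ITT analysis of both primary endpoints is defeated. That does not follow either. Modest removal equal by arm leaves the hazard ratio essentially unchanged, removal at recurrence loses no RFS event that has already been documented, and nothing shows that anyone has been removed.

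The reply does not remove the conflict. The narrow reading still takes in any drug whose package insert warns of hepatotoxicity. The vital-status checks recover no imaging, and the text does not say whether someone removed still counts as a participant to be contacted.

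**Conclusion.** Wrong as written. One sentence in Section 6.5 contradicts its own opening, Sections 7.1 and 7.2, and the synopsis. Followed literally, it can cause avoidable loss of RFS and OS follow-up, and so can weaken the ITT analyses.

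The size cannot be determined. The documents give no removal frequency, the scope of the sentence is ambiguous, and the RFS censoring rules are redacted. The loss is negligible if the sentence is rarely applied. Under the stated assumptions, bias in the hazard ratio at modest removal rates needs removal that differs by arm; it then reaches about 0.02 to 0.05 on a null RFS ratio when the excess is on pembrolizumab. Equal removal mainly costs events and, for OS, overstates the survival curves. The removal rates, the link to prognosis, the hazard ratios and survival after recurrence are all assumed.

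**What to change.** Reconcile Sections 6.5, 7.1 and 7.2. In 6.5, replace the instruction to remove participants with a statement that, absent withdrawal of consent, those who need a treatment named in the section remain in the study and continue imaging, RFS and survival follow-up under Sections 8.11.2.2, 8.11.2.3 and 8.11.3. Applied to both lists, this means the scope of the sentence no longer affects retention of data.

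Ask sites to identify anyone already removed under this sentence, and restore follow-up where consent allows.

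Whether and when study intervention stops for each listed treatment is a separate question. The opening of 6.5 and Section 7.1 differ on it, and the sponsor must reconcile them; no rule is proposed here.

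The cost is one sentence in an amendment and a letter to sites. No new assessments are needed.
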